3. DESIGN AND PROCEDURES

3.1 Study duration

Total involvement for each participant will be 16 weeks. Each diet will be followed for 44 days (4 day rotating menus x 11 periods) with a 14-day washout period in between.

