3.3 Study Schedule

ACTIVITY/VISIT	WEEK	DURATION
PHONE SCREEN A scripted phone screen will be performed to determine pre-eligibility prior to consent.	1	15 min
CONSENT A one-on-one consent visit will be conducted privately with staff either in-person or via Zoom.	1	1 h
SCREENING This visit will take place in the morning after an overnight fast and will have the following procedures: informed consent, screening blood draw (including serum pregnancy test for women of child-bearing potential), health history, height and weight, and screening questionnaires regarding food intake, health, and sleep.	1	2 h
BASELINE VISIT DIET 1 This visit will take place in the morning after an overnight fast. Participants will be asked to complete a fasted blood draw and questionnaires, and bring in urine and stool samples that were collected using at-home collection kits.	2	1 h
INTERVENTION DIET 1 Participants will be randomized to consume one of the following sourced diets: agroecological or conventional. They will follow this nutrition pattern for 44 days. During this time, participants will come to the NDFS building twice a week to pick up food.	2-8	1 h per week
POST VISIT DIET 1 On the last day of diet 1, participants will be asked to complete a fasted blood draw and questionnaires, and bring in urine and stool samples that were collected using at-home collection kits.	8	1 h
WASHOUT PERIOD Participants will consume self-selected (habitual) diets for 14 days. No involvement from research team.	9-10	none
BASELINE VISIT DIET 2 This visit will take place in the morning and will have a fasted blood draw. Participants are also asked to bring in stool and urine samples that were collected using at-home collection kits.	10	1 h
INTERVENTION DIET 2 Participants will now start their second nutritional intervention (agroecological or conventional sourced diet depending on the diet consumed during the first intervention). During this time, participants will come to the NDFS building twice a week to pick up food.	10-16	1 h per week

POST VISIT DIET 2 On the last day of diet 2, participants will be asked to complete a fasted blood draw and questionnaires, and bring in urine and stool samples that were collected using at-home collection kits.	16	1 h
---	----	-----

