- **Sleep, diet, and activity logs:** We will ask participants to maintain their habitual sleep levels. Participants will be asked to log their wake-up and sleep time as well as the time they spend doing physical activity in RedCap. Participants will be provided a daily link and/or reminded by phone (only if they forgot to fill these out).
- **Stool and urine samples:** Additional stool and urine samples will be collected at the end and beginning of each dietary period, using a similar approach as described in the *baseline visit 1* subsection,
- **Activity:** We will ask participants to maintain their habitual physical activity levels. A commercial Garmin activity monitor will be worn 24 hr/d to record total daily steps as a measure of physical activity. The activity monitor will connect via Bluetooth to the participant's personal smartphone or other internet-connected device loaded with the Garmin Connect app. Data will be stored in individual study accounts on the Garmin website where the study team will be able to access and review activity and monitor device function and provide feedback and encouragement to participants.

Post Diet Visits 1-2 (Weeks 8 & 16; 1 hour): On the last day of each nutrition intervention/diet phase, participants will be asked to come to the CHNS building at Utah State University to undergo a fasted blood draw (30 mL), and to complete questionnaires to determine intervention effects. The blood will be used for cytokines and metabolites and for routine blood samples analysis by LabCorp as described in the *screening visit subsection*. The questionnaires involved include the Perceived Stress Scale (PSS), Short Form Healthy Survey (SF-36), Profile of Mood States (POMS), and the Pittsburgh Sleep Quality Index (PSQI).

Baseline Visit 2 (weeks 8; 1 hour): At the beginning of the second 44-day dietary intervention period, participants will report to the lab facilities within the Center for Human Nutrition at Utah State University after an overnight fast (no eating or drinking except water for 12 h). Participants will be asked to collect fasting urine and first-of-the-day stool samples the morning before coming in, and will undergo a fasted blood draw (30 mL) while in the lab. The blood will be

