7. ANALYTICAL PROCEDURES AND STATISTICAL CONSIDERATIONS

- **Inflammation:** Inflammatory biomarkers (IL-6, VCAM-1, TNF-alpha and C-reactive protein [CRP]) will be measured using ELISA kits at Dr. [name]'s laboratory at Utah State University. Plasma samples will be stored at -80°C until cytokine analyses are performed.
- **Dietary logs:** The Diet History Questionnaire III (NIH) and 7-day food records will be analyzed by dietetic staff within Dr. [name]'s laboratory at Utah State University.
- **Metabolomics:** Mass spectrometry techniques will be used for untargeted and/or targeted assessment of blood and/or urinary metabolites. This analysis will give insight into the appearance of food-derived metabolites in the human body and how they may impact biomarkers of human health. This analysis will be performed using de-identified samples by Metabolon Inc (a company dedicated to metabolomics analysis) and/or the Plants for Human Health Institute. Samples will be provided to these core services as de-identified samples. No other data will be shared with these core services. Plasma and urine samples will be stored at -80°C until metabolomics analyses are performed.
- **Gut microbiome taxonomy:** DNA will be extracted from stool samples using a QIAamp Fast DNA Stool Mini Kit following manufacturer's instructions and analyzed for taxonomic assignment using 16s rRNA sequencing at Utah State University's Genomics Core. Samples will be provided to the core service as de-identified samples. No other data will be shared with the core service.

- **Statistical analysis:** Change scores (post-dietary intervention – baseline) will be created for all inflammatory biomarkers and metabolites. Metabolic intermediate data will be reduced into Metabolic Factors using Principal Component Analysis (PCA) of the change scores. Factor scores will be computed for each individual for both diets. Change scores and factor (change) scores for both diets will be compared using paired t-tests. $P < 0.05$ will be considered statistically significant and analyses will be performed in SAS 9.4 (SAS, Cary, NC).

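### Section 3.4 puts Baseline Visit 2 in week 8, as diet 1 ends, but Section 3.3 puts it in week 10; the change-score endpoint depends on which is used, and no carry-over check is planned

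*Combined protocol and SAP*

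**What the plan says.** All references are to the combined protocol and SAP.

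- Section 3.4 on the second baseline: "Baseline Visit 2 (weeks 8; 1 hour): At the beginning of the second 44-day dietary intervention period". Its text adds that the first diet-2 food box is handed out at this visit.
- Section 3.4 on the endpoint visits: "Post Diet Visits 1-2 (Weeks 8 & 16; 1 hour): On the last day of each nutrition intervention/diet phase". Post Diet Visit 1 and Baseline Visit 2 therefore carry the same week, 8.
- Section 3.3 has a row beginning "BASELINE VISIT DIET 2 This visit will take place in the morning and will have a fasted blood draw", with week 10 in its week column. The washout row above it covers weeks 9-10 and reads "Participants will consume self-selected (habitual) diets for 14 days. No involvement from research team".
- Section 3.1: "Each diet will be followed for 44 days (4 day rotating menus x 11 periods) with a 14-day washout period in between". Sections 1, 3.3 and 3.4 give the same 14 days.
- Section 7: "Change scores (post-dietary intervention – baseline) will be created for all inflammatory biomarkers and metabolites". The two diets' change scores are then compared by paired t-test. No period, sequence or carry-over term is named, and no check that participants return to baseline.

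**The concern.** The second baseline is half of the diet-2 endpoint. Anything left over from diet 1 when that sample is drawn is subtracted from the diet-2 change. Averaging over the two sequences does not cancel this, because in each sequence the residue pushes the estimated difference away from zero in proportion to the first diet's own effect. A draw in the week diet 1 ends would carry most of that effect; a draw after the washout would carry less.

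Two things are at stake: an operative visit week that conflicts with the schedule, and a change-score estimate whose size depends on a return to baseline that the plan does not examine, although blood for cytokines and metabolites is drawn at both baselines.

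**Working it through.** **Day count.** Inputs: diet 1 starts in week 2 (Sections 3.3 and 3.4), so on one of days 8 to 14; 44 days per diet and a 14-day washout (Section 3.1). Week = floor((day − 1)/7) + 1.

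- Start on day 8: diet 1 ends on day 8 + 43 = 51, week 8. This reproduces the Post Diet Visit 1 week.
- Washout is days 52 to 65, so Baseline Visit 2 falls on day 66: floor(65/7) + 1 = week 10. This reproduces Section 3.3.
- Diet 2 ends on day 66 + 43 = 109: floor(108/7) + 1 = week 16. This reproduces both sections.
- Starts on days 9 to 14 put Baseline Visit 2 on days 67 to 72, week 10 or 11. No week-2 start gives week 8.
- Week 8 ends on day 56, so with a day-8 start a week-8 draw comes at most 56 − 51 = 5 days after diet 1 stops.

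**Effect on the contrast.** Set the habitual level to 0. Let a and c be the effects of the agroecological and conventional diets at the end of a period, and L the fraction of the diet-1 effect present at Baseline Visit 2. Take diet-1 residue at the end of diet 2 as negligible.

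- Agroecological first: a − (c − L·a) = (a − c) + L·a
- Conventional first: (a − L·c) − c = (a − c) − L·c
- Average with equal sequences: (a − c)(1 + L/2)

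L = 0 gives 1.0. L = 1 gives 1.5, so the planning difference of 0.157 in the power calculation would be estimated as 0.157 × 1.5 = 0.2355. If a = c the average is zero. In a simulation with n = 34, equal sequences, L = 1 and no true difference (20,000 runs per case), the two-sided 0.05 test rejected in 0.018 to 0.050 of runs.

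**Unequal sequences.** Section 3.4 gives no allocation ratio. With a proportion p starting on the agroecological diet, the contrast is (a − c) + L[p·a − (1 − p)·c]. For L = 1, a = 0.457 and c = 0.3:

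- p = 0.6: (0.157 + 0.2742 − 0.12)/0.157 = 1.98
- p = 0.4: (0.157 + 0.1828 − 0.18)/0.157 = 1.02

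With a = c = 0.2, p = 0.6 and L = 1, the contrast is 0.12 − 0.08 = 0.04 although the diets are equal.

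**Size by timing.** Assume first-order return with half-life h, equal sequences, and a gap of g days between the end of diet 1 and the draw, with diet 2 starting at the draw. Let w = 2^(−g/h) and k = 2^(−44/h). The change-score factor is 1 + w(1 − k)/2; the factor for a contrast of post-diet values is 1 − kw/2. Example, h = 7 and g = 14: w = 0.25, k = 0.0128, factor = 1 + 0.25 × 0.9872/2 = 1.12.

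| Gap and contrast | h = 3 d | h = 7 d | h = 14 d |
|---|---|---|---|
| 0 days, change score | 1.50 | 1.49 | 1.44 |
| 5 days, change score | 1.16 | 1.30 | 1.35 |
| 14 days (as scheduled), change score | 1.02 | 1.12 | 1.22 |
| 14 days (as scheduled), post-diet values | 1.00 | 1.00 | 0.97 |

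The first two rows drop the washout altogether. If only the draw were early and the washout were kept, the factor would be 1 + (w − k·w14)/2, where w14 is the fraction left at 14 days. For h = 14 and g = 0 that is 1 + (1 − 0.1132 × 0.5)/2 = 1.47, close to the 1.44 shown. The half-lives are assumptions; the documents give none.

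**The case against.** The strongest reply is that week 8 is a slip that nobody would follow. The sentence carrying it places the visit at the start of the second diet period, the food box is handed over there, the 14-day washout is stated in four sections, and counting 44 days back from the week-16 endpoint leads to week 10. The study runs at a single centre, so there are no independent sites to misread it. This largely stands: a wrong label is the likeliest explanation. It does not remove the need to correct the visit description, which staff may use to book the draw.

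A second reply is that carry-over at 14 days is a separate matter resting on assumed kinetics. That also stands. A reader might infer from the factors of 1.02 to 1.22 that the washout is too short, but no figure in the documents shows carry-over at 14 days. What remains is that Section 7 plans no look at it, although the samples exist.

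Third, with 18 completers (the Section 4.1 goal) to 34 (the power calculation), or about 9 to 17 per sequence if split equally, a baseline comparison by sequence is imprecise, and change-score and post-diet estimates will differ by chance alone. This is right. It rules out treating any gap between the two estimates as proof of carry-over, or discounting the excess automatically, since no threshold could be defended.

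**Conclusion.** The contradiction is certain: Section 3.4 says week 8, Section 3.3 says week 10, and the stated durations reproduce only the latter. The sections must be reconciled.

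The effect on results is conditional. A reader might infer that the trial will overstate its diet difference by half. The documents do not support that: the factor of about 1.5 needs the week-8 label to be followed with essentially the whole diet-1 effect still present, equal sequences, and negligible diet-1 residue at the end of diet 2. Nor is 1.5 a general ceiling, because with unequal sequences the factor can lie on either side of it. On the schedule as Section 3.3 has it, the factor is 1.02 to 1.22 across the three assumed half-lives.

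A reader might also infer a raised false-positive rate. With equal sequences and no true difference the bias is zero, and the simulation showed no inflation. The issue is then the size of a real difference, not the creation of a false one.

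**What to change.** 1. Reconcile the week of Baseline Visit 2 between Sections 3.3 and 3.4, and express it as a day count from the last day of diet 1, so that the stated washout precedes the draw.
2. In Section 7, prespecify the paired comparison of post-diet values as a sensitivity analysis beside the change-score comparison. Under the model above it is nearly free of carry-over at the scheduled gap (0.97 to 1.00).
3. Report Baseline 2 minus Baseline 1 by sequence with confidence intervals, labelled as a descriptive, low-precision check and not a decision rule.

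The cost is one corrected visit week and a few lines of analysis text, with no new samples or visits. The downside is that the reported diet difference may be smaller than the change-score figure alone.

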4. SUBJECT RECRUITMENT AND COMPENSATION

4.1 Recruitment

Subjects will be recruited by posting flyers in designated areas around USU's campus, and through advertisement on public Facebook pages (Cache Valley Classifieds and/or Marketplace), local NextDoor pages, Craigslist, Reddit (R/Logan), Instagram, and/or Twitter. In the advertisement, potential subjects for this study will be directed to contact the study team by email or phone to obtain more information about the study, if interested. Participants who are interested will be provided with a copy of the informed consent by email. When the participant expresses interest in being in the study, the study team member will confirm, by telephone, that the participant meets most of the inclusion/exclusion criteria (ones that can be determined without the need for a blood draw) before scheduling him/her for a consent meeting. Subjects will attend a one-on-one information/consent session that will be conducted by a trained member to present the details of the study. We anticipate that we will need to telephone screen approximately 150 people and that approximately 30 will be consented. We will enroll up to 40 participants to meet our goal of having at least 18 participants complete the study.

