- **Power Calculations:** Using untargeted metabolomics for our power calculations of the number of participants we need to recruit, we assume a P -value ≤ 0.05 , Q -value ≤ 0.3 , and standard deviation of 0.3 based on previous work^{7,8}. 600 metabolites are typically identified and a conservative estimation in longer-term dietary intervention trials is that 40-80 metabolites will be significantly different with a mean of 0.157 (18 % difference). An $n=34$ per group is expected to provide true discovery rates ranging from 89-93 % assuming differences in 40-80 metabolites. Assuming a drop-out of 25%, the final number of participants we anticipate to recruit is $N=40$.

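### Section 4.1 sets a completion goal of at least 18 while Section 7 states its performance only at n=34, so the trial could meet its own goal without the performance it claims

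*Combined protocol and SAP*

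**What the plan says.** Section 4.1 (Recruitment) sets the completion goal: "We will enroll up to 40 participants to meet our goal of having at least 18 participants complete the study". Forty is a ceiling there and 18 a floor. The sentence before it forecasts recruitment: "We anticipate that we will need to telephone screen approximately 150 people and that approximately 30 will be consented".

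Section 7 (Power Calculations) sizes the study on untargeted metabolomics. Its inputs are P ≤ 0.05, Q ≤ 0.3, "and standard deviation of 0.3 based on previous work", 600 metabolites of which 40-80 are taken to differ, and a mean difference of 0.157. The claim is that n=34 "per group is expected to provide true discovery rates ranging from 89-93" %. Section 7 then says "Assuming a drop-out of 25%, the final number of participants we anticipate to recruit is" 40.

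Section 3.2 (Participants) plans to include 40 adults in all. The statistical analysis paragraph of Section 7 compares change scores between the two diets by paired t-test. Neither document section gives a reason for 18, or any power or discovery rate at 18.

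**The concern.** The protocol holds two completer figures that cannot come from one plan. Section 4.1 counts the study as having met its goal at 18 completers, which is 53% of the 34 at which Section 7 states what the study can detect. A study that finished with 18 would comply with Section 4.1, yet Section 7 says nothing about what it could find. A null result from 18 people would then be read against a claim made for 34. The drop-out assumption does not bridge the gap, because 25% loss from 40 leaves many more than 18.

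**Working it through.** **Inputs.** From Section 7: difference 0.157, SD 0.3, P ≤ 0.05, Q ≤ 0.3, 600 metabolites with 40-80 truly different, n=34, drop-out 25%, N=40, paired t-test. From Section 4.1: at least 18 completers, at most 40 enrolled. Two points are not stated and are assumed here: the test is two-sided, and 0.3 is the SD of the within-person difference. The second assumption is relaxed below.

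**The plan's own figure.** We could not reproduce 89-93% at n=34.
- Read as one minus the false discovery rate at P ≤ 0.05, the rate is m1·power / (m1·power + m0·0.05), with m1 metabolites truly different and m0 = 600 − m1. Power is 0.842 at n=34. With 40 true: 33.7/(33.7 + 28) = 54.6%. With 80 true: 67.3/(67.3 + 26) = 72.1%.
- Read as average power at the P threshold that gives a false discovery rate of 0.3, it is 74.3% (40 true) to 85.5% (80 true).
- One-sided paired power is 91.0%, inside the stated range, but it is not a discovery rate and does not vary with the 40-80.

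The comparison below therefore uses Section 7's inputs and not its stated result.

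**Completer arithmetic.**
- 40 × (1 − 0.25) = 30 completers expected from 40 enrolled.
- 1 − 18/40 = 55% loss implied by 18 completers from 40.
- 18/0.75 = 24 enrolled would already give 18 completers at 25% drop-out.
- 34/0.75 = 45.3, so 46 enrolled would be needed for 34 completers. Forty gives 34 only if drop-out is 1 − 34/40 = 15%.

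**Power per metabolite.** Noncentral-t power of a paired t-test, df = n − 1, noncentrality = (0.157/SD)·√n, two-sided 0.05. With SD 0.3 the standardised difference is 0.157/0.3 = 0.523. If 0.3 is the SD within each diet and values on the two diets are uncorrelated, the SD of the difference is 0.3·√2 = 0.424 and the standardised difference is 0.370.

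| Completers | Noncentrality, SD 0.3 | Power, SD 0.3 | Noncentrality, SD 0.424 | Power, SD 0.424 |
|---|---|---|---|---|
| 18 | 2.22 | 55.3% | 1.57 | 31.7% |
| 30 | 2.87 | 79.1% | 2.03 | 50.0% |
| 34 | 3.05 | 84.2% | 2.16 | 55.4% |

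With SD 0.3, the difference detectable with 80% power is 0.210 at n=18 and 0.149 at n=34. The first is about a third larger than 0.157 (0.210/0.157 = 1.34).

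**With both cut-offs.** Take the P threshold at which m0·a/(m0·a + m1·power(a)) = 0.3, capped at 0.05, with SD 0.3 for the paired difference. Average power across 40 to 80 true differences is 25.0-46.1% at n=18, 65.9-79.1% at n=30 and 74.3-84.2% at n=34. Solving for the Benjamini-Hochberg threshold with independent tests gives 22.7-40.4% at 18 and 72.7-82.9% at 34.

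**The case against.** The strongest reply is that 18 is only a minimum acceptable yield. Section 3.2 plans for 40 participants and Section 7 anticipates recruiting 40, so the plan expects about 30 completers, not 18. That stands. A reader might infer from Section 4.1 that recruitment stops once 18 have finished, or that 55% is the planned power. The documents support neither: they contain no such rule.

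A reader might also take 84% as the protocol's claim, with 55% as the shortfall from it. It is not. Section 7 claims a true discovery rate and states no power per metabolite; both percentages are our calculations.

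Nor are those percentages firm. Section 7 does not say what the 0.3 is the SD of, and its per-group wording points away from the paired reading. The alternative column shows that both can fall by more than 20 points. What survives is the direction: 18 is well below 34 on every reading tried.

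Last, it is tempting to say that 34 should simply replace 18 in Section 4.1 at no cost. With 40 enrolled and 25% drop-out, that would write in a goal the plan expects to miss.

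None of this reconciles the sections. A stated goal of 18 still sits 12 below the yield that the plan's own drop-out rate implies, with no performance attached to it.

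**Conclusion.** The inconsistency is real and in the current text. The completion goal in Section 4.1 can be met by a trial that lacks the performance stated in Section 7. In the worst case that still meets the goal, power per metabolite is about 24 points below that at the 30 completers the plan implies (79.1 − 55.3) and about 29 below that at n=34 (84.2 − 55.3). This assumes a two-sided unadjusted 0.05 and 0.3 as the SD of paired differences. With 0.3 as an uncorrelated SD within each diet, the gaps are about 18 points (50.0 − 31.7) and 24 points (55.4 − 31.7). The contradiction between 18, 34 and a 25% loss from 40 needs none of these assumptions. The finding concerns what the protocol promises; it does not predict that the trial will end with 18.

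**What to change.** Use one completer figure in both sections, without enrolling beyond 40.

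- Section 4.1: write 40 as the planned enrolment in place of a ceiling, in line with Section 3.2, and replace the goal of at least 18 with the 30 completers that 40 enrolled and 25% drop-out imply.
- Section 7: restate the performance at n=30, say whether 0.3 is the SD of paired differences or the SD within each diet, and show how the true discovery rate is obtained.
- If 18 is a real minimum, keep it, label it as such, and state the Section 7 performance at n=18 as well.
- Bring the forecast of about 30 consented into line, since 30 completers from 30 consented would leave no room for drop-out.

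The cost is a few sentences and a less favourable stated performance: on our figures about 79% in place of 84% per metabolite, or 50% in place of 55% on the alternative reading of the SD. Keeping 34 as the completer goal is possible only with about 46 enrolled or with drop-out assumed at 15%, and the protocol would have to say which.
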